## Attachment 2. Protocol ABET Clinical Laboratory Tests

---

### Clinical Laboratory Tests

---

#### Hematologya

Hemoglobin  
 Hematocrit  
 Erythrocyte count (RBC)  
 Leukocytes (WBC)  
 Platelets  
 Neutrophils, Segmented  
 Lymphocytes  
 Monocytes  
 Eosinophils  
 Basophils

#### Other

Pregnancy testb  
 Hemoglobin A1ca  
 Anti-Glargine Antibodiesa  
 Serum for Biomarkers Nonpharmacogenetic  
 Biomarkers (C-peptide)

#### Clinical Chemistrya

##### Serum Concentrations of:

Sodium  
 Potassium  
 Total bilirubin  
 Direct bilirubin  
 Indirect bilirubin  
 Alkaline phosphatase  
 Alanine aminotransferase (ALT)  
 Aspartate aminotransferase (AST)  
 Blood urea nitrogen (BUN)  
 Creatinine  
 Albumin

##### Fasting serum glucose

---

Abbreviations: RBC = red blood cell; WBC = white blood cell

a All laboratory tests to be performed at a central laboratory, unless specified otherwise.

b Serum pregnancy tests will be performed on all females of childbearing potential at Visit 1 (and when clinically indicated) and will be analyzed by the central laboratory. Urine pregnancy tests at other visits can be accepted per local regulations. A urine pregnancy test may be repeated locally for any visits if considered necessary by the investigators and/or in compliance with local regulations.

## Attachment 3. Protocol ABET Estimated Sampling Summary

This table summarizes the purpose for sampling, sample types, estimated volume per sample, number of samples, and estimated total volume during the study.

### Protocol I4L-GH-ABET Sampling Summary

Purpose	Sample Type	Estimated Amount per Sample	Number Samples	Estimated Total Amount
Screening tests a	Blood	3 mL	2	6 mL
Standard laboratory tests a	Blood	3 mL	9	27 mL
Immunogenicity samples	Blood	8 mL	5	40 mL
Nonpharmacogenetic biomarkers (C-peptide)	Blood	6 mL	3	18 mL
Total				91 mL
Hepatic Monitoring b	Blood	-	-	3 - 30 mL

a Additional samples may be drawn if needed for safety purposes.

b Based on laboratory safety values, unscheduled hepatic monitoring testing may be performed as part of patient follow-up, in consultation with Lilly Designated Medical Monitor.

---

## Attachment 4. Protocol ABET Hepatic Monitoring Tests for Treatment Emergent Abnormality

---

### Hepatic Monitoring Tests

#### Hepatic Hematologya

Hemoglobin  
 Hematocrit  
 RBC  
 WBC  
 Neutrophils, segmented  
 Lymphocytes  
 Monocytes  
 Eosinophils  
 Basophils  
 Platelets

#### Hepatic Chemistrya

Total bilirubin  
 Direct bilirubin  
 Alkaline phosphatase  
 ALT  
 AST  
 GGT  
 CPK

#### Haptoglobina

#### Hepatic Coagulationa

Prothrombin Time  
 Prothrombin Time, INR

#### Hepatic Serologiesa,b

Hepatitis A antibody, total  
 Hepatitis A antibody, IgM  
 Hepatitis B surface antigen  
 Hepatitis B surface antibody  
 Hepatitis B Core antibody  
 Hepatitis C antibody  
 Hepatitis E antibody, IgG  
 Hepatitis E antibody, IgM

#### Anti-nuclear antibodya

#### Anti-smooth muscle antibodya

Abbreviations: ALT = alanine aminotransferase; AST = aspartate aminotransferase; CPK = creatine phosphokinase; GGT = gamma-glutamyl transpeptidase; IgG = Immunoglobulin G; IgM = Immunoglobulin M; INR = international normalized ratio; RBC = red blood cells; WBC = white blood cells.

a Assayed by Lilly-designated central laboratory

b Reflex/confirmation dependent on regulatory requirement and /or testing availability.

---

## Attachment 5. Protocol ABET World Health Organisation (WHO) Classification of Diabetes

---

**Type 1 Diabetes Mellitus:** Type 1 diabetes mellitus is judged to be present when the classical symptoms of diabetes (thirst, polyuria, wasting and stupor, or coma) are associated with readily detectable concentrations of glucose and ketone bodies in the blood and urine. Insulin treatment is necessary, not only to control hyperglycaemia, but to prevent spontaneous ketosis and death.

**Type 2 Diabetes Mellitus:** Type 2 diabetes mellitus, although often asymptomatic, may also present with classical hyperglycaemic symptoms (thirst, polyuria, weight loss), but despite hyperglycaemia, ketone bodies are present in only low concentrations in the blood and urine. Coma is rare in type 2 diabetes, but may result from extreme hyperglycaemia and hyperosmolarity; lactic acidosis or ketoacidosis can also occur in fulminating illness (for example, severe infection or mesenteric artery thrombosis) due to an acute increase in insulin requirements, but spontaneous ketosis does not occur. Some patients with type 2 diabetes later progress to a state of absolute insulin deficiency (Bennett 1991).

---

**Attachment 6. Protocol Amendment I4L-GH-ABET(a)  
Summary: A Prospective, Randomized, Open-Label  
Comparison of a Long-Acting Basal Insulin Analog  
LY2963016 to Lantus® in Adult Chinese Patients with Type  
2 Diabetes Mellitus**

---

## Overview

Protocol I4L-GH-ABET has been amended. The new protocol is indicated by amendment (a) and will be used to conduct the study in place of any preceding version of the protocol.

The overall changes and rationale for the changes made to this protocol are as follows:

- Estimated first patient visit and last patient visit in synopsis were updated.
- Visit 801 was changed from telephone visit to clinic visit to mitigate the risk of source data inaccuracy.
- For patients who discontinue from the study, completion of Visit 801 was added to avoid missing of Visit 801.
- Tests of fasting serum glucose at Visit 2, Visit 18 or ED were added in study schedule (Attachment 1) as a complementation of self-monitored blood glucose (SMBG) pre-morning value and c-peptide in data interpretation. And in Attachment 2, fasting serum glucose was added.
- For serious adverse events after study completion or patient discontinuation in Section 10.3.1.1, related paragraph was updated according to current protocol template (version 11.0).
- Infuse database is no longer in use, so it was replaced by Clintrial.
- For treatment-emergent adverse event, the definition was revised from events newly reported or worsened after randomization to those after first study treatment to exclude events occurred or worsened after randomization and prior to first dose. Definition of TEAE in Section 4 was also updated per current clinical protocol template (version 11.0).
- In Attachment 3, estimated sampling for standard laboratory test was updated, and total amount was changed accordingly.
- For hepatic safety monitoring in Section 10.3.3, elevated ALT or AST > 3X ULN or elevated total bilirubin > 2X ULN was changed to elevated ALT or AST ≥ 3X ULN or elevated total bilirubin ≥ 2X ULN.

## Revised Protocol Sections

**Note:** Deletions have been identified by ~~strikethroughs~~.  
Additions have been identified by the use of underscore.

### 2. Synopsis

#### Length of Study:

Estimated first patient visit: Mar 2017~~8~~ Estimated last patient visit: Feb 2019~~20~~

### 4. Abbreviations and Definitions

#### ~~treatment emergent adverse event (TEAE)~~

[figure not shown]
[figure not shown]
~~Any untoward medical occurrence that either occurs or worsens at any time after treatment baseline and that does not necessarily have a causal relationship with this treatment.~~ Treatment-emergent adverse event: An untoward medical occurrence that emerges during a defined treatment period, having been absent pretreatment, or worsens relative to the pretreatment state, and does not necessarily have to have a causal relationship with this treatment.

### 7.1. Summary of Study Design

At approximately 4-week post-treatment endpoint (Visit 801), patients will have a final ~~telephone~~clinic visit at which information will be collected according to the Study Schedule (Attachment 1). The starting dose is 10 units (U), which will be titrated by the weekly dosing algorithm as described in Section 9.5 until fasting blood glucose (FBG) reaches  $\leq 100$  mg/dL (5.6 mmol/L) (weekly-base titration till Visit 10 and titration as needed afterwards. The insulin doses can be adjusted between intervals at discretion of the investigators. The titration procedure during the study will occur as described in Section 9.5.

End of study (trial) is the date of the last visit or last scheduled procedure shown in the Study Schedule for the last active patient in the study.

Figure ABET.7.1 illustrates the study design.

**7.2.2.4. Follow-up Visit (Visit 801)**

Patients will receive a telephone call or come to the investigator site approximately 4 weeks after the last treatment visit, at which time information will be discussed and recorded according to the

Study Schedule (Attachment 1). Note: The previous day's insulin dose will be recorded if the patient has continued to take insulin.

Patients who discontinue early from the study will undergo all the end of study procedures and complete Visit 801 as outlined in Attachment 1.

#### **10.3.1.1. Serious Adverse Events**

~~The investigator does not need to actively monitor patients for adverse events once the trial has ended, unless provided otherwise in the protocol. However, if an investigator becomes aware of SAEs occurring to a patient after the patient's participation in the trial has ended, the investigator should report the SAEs to the sponsor, regardless of the investigator's opinion of causation, and the SAEs will be entered in the pharmacovigilance system at the sponsor. Investigators are not obligated to actively seek AEs or SAEs in subjects once they have discontinued and/or completed the study (the patient summary CRF has been completed). However, if the investigator learns of any SAE, including a death, at any time after a subject has been discharged from the study, and he/she considers the event reasonably possibly related to the study treatment or study participation, the investigator must promptly notify Lilly.~~

#### **10.3.3. Safety Monitoring**

If a study patient experiences elevated ALT or AST  $\geq 3$ X ULN or elevated total bilirubin  $\geq 2$ X ULN, clinical and laboratory monitoring should be initiated by the investigator. Details for hepatic monitoring depend upon the severity and persistence of observed laboratory test abnormalities. To ensure patient safety and comply with regulatory guidance, the investigator is to consult with the Lilly designated medical monitor regarding collection of specific recommended clinical information and follow-up laboratory tests. See Attachment 2 and Attachment 4.

#### **10.4.2.1. Nonpharmacogenetic Biomarker Evaluations**

This study will employ sample collection. Samples will be collected for nonpharmacogenetic biomarker investigation where local regulations allow. ~~Blood~~Fasting serum samples will be collected at the times specified in the Study Schedule (Attachment 1).

Fasting samples being collected will be used to measure C-peptide to support trial interpretation.

#### **12.2.4. Concomitant Therapy**

Concomitant medications, including previous therapies for diabetes, will be summarized by different categories and treatment group using the FAS population. All concomitant therapies that originally mapped using the WHODRUG dictionary in the ~~InFuse~~Clintrial database will be further classified using anatomical, therapeutic chemical code for reporting purpose. Analyses will use test Fisher's Exact Test or Pearson's Chi-square test.

**12.2.9.3. Adverse Events**

Adverse events will be listed by patient, system organ class, Medical Dictionary for Regulatory Activities® (MedDRA) preferred term, severity, and relationship to the study disease, drug, device, or procedure for all patients. Adverse events will be summarized as treatment-emergent adverse events (TEAEs) for the FAS. Treatment-emergent adverse events are defined as events that are newly reported after first study treatment following randomization, or reported to worsen in severity from randomization baseline. The proportion of patients experiencing each TEAE will be presented by preferred term, system organ class, and treatment group. The proportion of patients experiencing each TEAE that are assessed as possibly related to the study disease, drug, device, or procedures will also be summarized. The number and proportion of patients will be presented and compared by treatment using Fisher's exact test or Pearson's chi-square test for the FAS.

**Attachment 1. Protocol ABET Study Schedule**

Description of Event	Visit																			
	1	2	3*	4	5*	6	7*	8	9*	10	11*	12	13*	14	15*	16	17*	18	801±	ED #
Week of Study	-2	0	1	2	3	4	5	6	7	8	10	12	14	16	18	20	22	24	28	
Allowable Deviation (days) a	±7		±3	±2	±3	±2	±3	±2	±3	±2	±3	±2	±3	±2	±3	±2	±3	±2	±7	
Telephone Visit			x		x		x		x		x		x		x		x		x	
Clinic Visit	x	x		x		x		x		x		x		x		x		x	x	x
Clinic Assessments																				
Concom Meds c,d	x	x	x c	x	x c	x	x c	x	x c	x	x c	x	x c	x	x c	x	x c	x	x d	x
Adverse Events c,d	x	x	x c	x	x c	x	x c	x	x c	x	x c	x	x c	x	x c	x	x c	x	x d	x
Hypoglycemic Episodes c,d		x	x c	x	x c	x	x c	x	x c	x	x c	x	x c	x	x c	x	x c	x	x d	x
4-pt SMBG c,d			x c		x c		x c		x c		x c		x c		x c		x c		x d	
Study Drug/Device																				
Distribute Study Diary	x	x		x		x		x		x		x		x		x		x		x
Transfer Diary Data to eCRF (InForm™)																				
Insulin Therapy Dose (day prior to visit)			x	x	x	x	x	x	x	x	x	x	x	x	x	x	x	x	x d	x
4-pt SMBG d,i				x i		x i		x i		x i		x i		x i		x i		x i	x d,i	x i
Lab Assessmentsi																				
Collection of Serum Samples for Biomarkers (Fasting) d		x d								x d								x d		xd
Fasting Serum Glucose d		xd																xd		xd

# Patients who discontinue early from the study will complete Visit 801.

c Adverse events, hypoglycemic episodes, concomitant medications and the last 3 available profiles of 4-point SMBG reported at telephone visits should be recorded on the eCRF at the next office visit, ~~or at Visit 801.~~ The 4 points are: before morning, mid-day, and evening meals, and at bedtime.

d ~~Information will be collected during a telephone visit and will be recorded on the eCRF. Site documentation will serve as the source for this telephone visit, as the patient will not be returning the paper diary to the site.~~ The measurements should be done fasting before breakfast.

**Attachment 2. Protocol ABET Clinical Laboratory Tests**

Hematologya	Clinical Chemistrya
Hemoglobin	Serum Concentrations of:
Hematocrit	Sodium
Erythrocyte count (RBC)	Potassium
Leukocytes (WBC)	Total bilirubin
Platelets	Direct bilirubin
Neutrophils, Segmented	Indirect bilirubin
Lymphocytes	Alkaline phosphatase
Monocytes	Alanine aminotransferase (ALT)
Eosinophils	Aspartate aminotransferase (AST)
Basophils	Blood urea nitrogen (BUN)
	Creatinine
Other	Albumin
Pregnancy test b	Fasting serum glucose
Hemoglobin A 1c a	
Anti-Glargine Antibodies a	
Serum for Biomarkers Nonpharmacogenetic	
Biomarkers (C-peptide)	

**Attachment 3. Protocol ABET Estimated Sampling Summary**

Purpose	Sample Type	Estimated Amount per Sample	Number Samples	Estimated Total Amount
Screening tests a	Blood	3 mL	2	6 mL
Standard laboratory tests a	Blood	3 mL	89	2427 mL
Immunogenicity samples	Blood	8 mL	5	40 mL
Nonpharmacogenetic biomarkers (C-peptide)	Blood	6 mL	3	18 mL
Total				8891 mL
Hepatic Monitoring b	Blood	-	-	3 - 30 mL

5.2.11.1.2. Assessment of Injection Site Adverse Events.....	14
5.2.11.2. Hypoglycemic Events.....	14
5.2.11.3. Laboratory Measures – Chemistry/Hematology Panel.....	16
5.2.11.4. Laboratory Measures – Insulin Antibodies.....	16
5.2.11.5. Vital Signs.....	18
5.2.11.6. Other Safety Measures.....	19
5.2.12. Subgroup Analyses	20
5.2.13. Interim Analyses	22
5.2.14. Exploratory Analysis.....	22
5.2.15. Required Analyses for the Clinical Trial Registry (CTR).....	22
6. Unblinding Plan	23

7. References	24
8. Appendices	25

Table of Contents

Appendix		Page
Appendix 1.	List of Allergic Reaction Terms.....	26
Appendix 2.	Estimation of Creatinine Clearance Using the Cockcroft-Gault and MDRD for the Approximation of Glomerular Filtration Rate (GFR).....	28

3. Revision History

SAP Version 1 was approved prior to the First Randomized Patient.

Version 2 of the SAP will be approved prior to the first unblinding of the clinical team and prior to the database lock.

The following changes have been incorporated:

- The imputation rule for missing scores in ITSQ is updated in section 5.2.10.1.
- The analysis of nonnocturnal hypoglycemia and pseudo hypoglycemia is deleted.
- Subgroup analysis of entry age (<75 , ≥ 75) and entry HbA_{1c} levels ($<7\%$, $\geq 7\%$) are deleted. BMI cut point changed from 28, 30 to 24, 28
- One more rule added to exclude subjects from Per Protocol Set: Missing HbA_{1c} at baseline and/or at primary endpoint (week 24; only for subjects who should have V18)
- The definition of TEAR is updated.
- The shift tables of total insulin antibody and cross reactive insulin antibody are deleted.
- The analysis concerning to the following hypoglycemic categories were deleted:
 - Severe hypoglycemia (BG level ≤ 70 mg/dL[3.9 mmol/L])
 - Severe hypoglycemia (not biochemically confirmed—BG missing)
 - Severe hypoglycemia (not biochemically confirmed—BG not aligned with severe symptoms)
 - Nonnocturnal hypoglycemia
 - Pseudo-hypoglycemia

4. Study Objectives

4.1. Primary Objective

The primary objective of this study is to test the hypothesis that LY2963016 administered QD is noninferior to Lantus[®] administered QD by a margin of 0.40%, as measured by change in hemoglobin A1c (HbA1c) from baseline to 24 weeks, when used in combination with OAMs.

4.2. Secondary Objectives

The secondary objectives of the study are as follows:

- To test the hypothesis that Lantus[®] is noninferior to LY2963016 (QD), as measured by change in HbA1c from baseline to 24 weeks, when used in combination with OAMs. (this secondary objective is tested with a gated approach).
- To compare safety of LY2963016 relative to Lantus[®] (proportion of patients with detectable anti-glargine antibodies, hypoglycemia, and injection site reaction) when used in combination with OAMs.
- To compare change in HbA1c at 4, 8, 12, 16, and 20 weeks between LY2963016 and Lantus[®] when used in combination with OAMs.
- To compare 7-point self-monitored blood glucose (SMBG) profiles (as plasma equivalent values) at 0, 2, 6, 12, and 24 weeks between LY2963016 and Lantus[®] when used in combination with OAMs.
- To compare percentage of patients with HbA1c <7% and percentage of patients with HbA1c ≤6.5% at 4, 8, 12, 16, 20, and 24 weeks between LY2963016 and Lantus[®] when used in combination with OAMs.
- To compare LY2963016 to Lantus[®] when used in combination with OAMs with regard to the following measures:
 - inpatient blood glucose (BG) variability
 - basal insulin dose
 - weight change
- To compare LY2963016 relative to Lantus[®] for patient-reported outcomes (PRO) as measured by responses to the Insulin Treatment Satisfaction Questionnaire (ITSQ).

5. A Priori Statistical Methods

5.1. Determination of Sample Size

Based on the primary objective, to show noninferiority of LY2963016 to Lantus[®] at the 0.40% noninferiority margin (NIM), 450 completers in total with a ratio 2:1 (LY2963016 versus Lantus[®]) are needed at 24 weeks. This calculation assumes no treatment difference in HbA1c between LY2963016 and Lantus[®], common standard deviation (SD) of 1.3% for change from baseline in HbA1c, 0.05 two-sided significance level, and over 85% power. Assuming a 15% dropout rate at 24 weeks, the required number of randomized patients is 530 in total (353 for LY2963016 and 177 for Lantus[®]).

5.2. Statistical and Analytical Plans

5.2.1. General Considerations

All data will be entered, verified, and archived by a contract research organization (CRO) external to Lilly and/or at Lilly. Data listings, summaries, and analyses will be performed by a CRO and/or by Lilly under the guidance and approval of statisticians at Lilly. Statistical analysis of this study will be the responsibility of Lilly.

Any change to the data-analysis methods described in the protocol will require an amendment ONLY if it changes a principal feature of the protocol. Any other change to the data analysis methods described in the protocol, and the justification for making the change, will be described in the statistical analysis plan and/or in the clinical study report (CSR). Additional exploratory analyses will be conducted as deemed appropriate.

The patient populations used in the study are described below:

1. All Patients Entered - all patients who signed ICF
2. All Randomized - all patients who were randomized to a treatment arm
3. Full Analysis Set (FAS) - based on the intent to treat (ITT) principle, all patients who were randomized and who have taken at least one dose of study medication will be included in this analysis set. Patients will be analyzed according to the treatments to which they were randomized.
4. Per-protocol (PP) - patients in the FAS/ITT population who also meet the criteria in Trial Issue Management Plan (TIMP), and treatment group will be defined on the basis of the treatment the patients actually receive:
 - a. have no violations of Inclusion/Exclusion Criteria specified in TIMP
 - b. have not discontinued from the study prior to 24 weeks
 - c. have not been off study medication for more than 14 consecutive days during the treatment period

- d. have not received chronic (lasting longer than 14 consecutive days) systemic glucocorticoid therapy (excluding topical, intra-articular, intraocular, and inhaled preparations)
- e. Missing HbA1c at baseline and/or at primary endpoint (week 24; only for subjects who should have V18)

Unless otherwise specified, listings will be prepared using all randomized patients. Efficacy and safety analyses will be conducted using the FAS population. Selected analyses will be conducted using the All Randomized population and the PP population.

Unless otherwise noted, all tests of treatment effects will be conducted at a 2-sided alpha level of 0.05, and confidence intervals (CIs) will be calculated as 2-sided 95% CIs. All tests of interactions between treatment groups and other factors will be conducted at a 2-sided alpha level of 0.05. No adjustments for multiplicity will be performed. See Section 5.2.7 for the gate-keeping strategies used for primary/secondary endpoints.

The baseline is Visit 2. If baseline data are missing, the last measurement taken prior to this visit will be used for the baseline measurement.

The last visit for the 24-week treatment study is Visit 18. If the Visit 18 measurement is missing, the last post-baseline value will be carried forward to create the 24-week endpoint value using the last-observation-carried-forward (LOCF) methodology. If there are no measurements after Visit 2 (date of randomization), the 24-week endpoint values will be considered missing. Efficacy analyses only be conducted for patients with both nonmissing baseline value and at least 1 nonmissing post-baseline value.

The LOCF methodology will be utilized in the endpoint analyses using analysis of covariance (ANCOVA) of HbA_{1c}, laboratory chemistry and hematology, as well as analysis of hypoglycemia (rate and incidence) and insulin antibodies.

Unless otherwise noted, the analysis of the continuous secondary efficacy and safety measurements (SMBG at each time point and summaries of SMBG, weight, dose, and vital signs) will use the same mixed model repeated measure (MMRM) methodology for the primary efficacy analyses with the baseline value of the response variable as a covariate with the FAS patient population. Continuous laboratory measures will be analyzed using an analysis of covariance (ANCOVA) model.

For categorical measures, Fisher's exact test will be used. To avoid computational problems, a maximum computation time of five minutes will be programmed into the analysis for Fisher's exact test. If it does not converge in that time, the Pearson's Chi-square test will be utilized.

Values for the 7-point self-monitored blood glucose (SMBG) blood glucose profiles will be averaged over the two 7-point SMBG profiles obtained during 2-week period prior to each office visit (as specified in Protocol Section 7.2.3). For the average blood glucose calculation for a specific time point, if only 1 of 2 days of data is collected, then the value of the 1 day will be used. If 2 days of data are collected, then the average of the 2 days will be used. If more than 2

days of data are collected then choose the 2 according to the ranking first by the number of non-missing blood glucose measurements and then by day closest to the visit day. The handling of missing data for the ITSQ questionnaire is specified in Section 5.2.10.

Visits for laboratory data will be handled by conventions in the Lilly diabetes white paper (Standardization of Derivations for Efficacy Lab Variables).

All analyses will be implemented using SAS Version 9.4® or higher.

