A first secondary analysis of the primary efficacy outcome will use the same MMRM model described above with the PP patient population. Significance tests will be based on LSMeans using the Type III sum of squares, and testing for noninferiority will occur as described above.

A second secondary analysis of the primary efficacy outcome will use an ANCOVA model with FAS population. The ANCOVA model will include treatment and entry use of insulin scretagogue (SU, meglitinide, neither) as fixed effects and the baseline value of HbA_{1c} as covariate. The ANCOVA model will be carried out using the OM option in SAS GLM procedure. If the 24-week HbA_{1c} value is missing, the last post-baseline value will be carried forward and used in the analysis. This creates the 24-week endpoint value for HbA_{1c} using the LOCF methodology. If there are no HbA_{1c} data after the date of randomization, the endpoint will be considered missing and the patient will not be included in the analysis.

The analyses of the primary efficacy outcome will only be conducted for patients with both nonmissing baseline value and at least 1 nonmissing post-baseline value.

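### Item 4(e) of the SAP's per-protocol definition has lost its negation: read literally, it admits only 24-week completers whose HbA1c is missing

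*SAP*

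**What the plan says.** SAP Section 5.2.1 introduces the PP set as "patients in the FAS/ITT population who also meet the criteria in Trial Issue Management Plan (TIMP"), followed by items (a) to (e). Items (a) to (d) are negated so that they fit this opening. Item (b), for example, is "have not discontinued from the study prior to 24 weeks". Item (e) is "Missing HbA1c at baseline and/or at primary endpoint (week 24; only for subjects who should have V18").

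The revision history in SAP Section 3 lists the same item among the Version 2 changes and labels it "One more rule added to exclude subjects from Per Protocol Set". Protocol Section 12.2.1 has only items (a) to (d), so it offers no alternative wording for (e).

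The PP set is put to use in SAP Section 5.2.7: "A first secondary analysis of the primary efficacy outcome will use the same MMRM model described above with the PP patient population". Noninferiority is tested there in the same way as in the primary analysis. SAP Section 5.2.3 also summarizes demographic and baseline characteristics for the PP set.

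**The concern.** An analysis-set definition is an instruction to a programmer. SAP Section 5.2.1 allows a contract research organization to run the analyses, so the written rule may be carried out by someone who did not draft it. Here the list says who is in, and item (e) names patients who should be out. Anyone applying all five items as conditions of entry would keep the patients that the rule was meant to remove, and would remove nearly everyone else.

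What is at stake is the first secondary analysis of the primary outcome in an open-label noninferiority trial, together with the PP baseline tables. The membership of that set should be reproducible from the SAP without a guess at the sign of one of its conditions.

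**Working it through.** **1. The plan's own sample size reproduces.** Inputs from SAP Section 5.1: margin 0.40, SD 1.3, true difference 0, two-sided alpha 0.05, 450 completers at 2:1 (300 and 150), 15% dropout.

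- SE = 1.3 × √(1/150 + 1/300) = 0.13.
- Power = Φ(0.40/0.13 − 1.96) = Φ(1.117) = 86.8% (86.7% with the noncentral t on 448 df). This agrees with the stated power of over 85%. The minimum for exactly 85% is 143 control patients, 429 in total.
- Randomized: 450/0.85 = 529.4, rounded up to 530, as stated.

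**2. Literal and intended PP sets.** Let m be the share of 24-week completers with missing HbA1c at baseline and/or Week 24. The documents give no value, so 0.5% to 10% is an assumed range. Item (b) limits both versions to completers.

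- Literal set = 450 × m.
- Intended set = 450 × (1 − m), before losses to items (a), (c) and (d).
- For a total of N patients at 2:1, SE = 1.3 × √(4.5/N) and power = Φ(0.40/SE − 1.96).

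| m (assumed) | Literal set | Nominal power | Intended set | Power |
|---|---|---|---|---|
| 0.5% | 2 | 4.1% | 448 | 86.6% |
| 1% | 5 | 4.9% | 446 | 86.5% |
| 2% | 9 | 6.4% | 441 | 86.1% |
| 5% | 23 | 10.2% | 428 | 85.1% |
| 10% | 45 | 16.2% | 405 | 83.1% |

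Patient counts are rounded; power uses the unrounded counts.

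**3. What the literal set could support.** The nominal power column is generous, because it treats every member as having a usable Week 24 change, and most or all would not. SAP Section 5.2.7 adds: "The analyses of the primary efficacy outcome will only be conducted for patients with both nonmissing baseline value and at least 1 nonmissing post-baseline value". Two cases follow.

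- *Missing at baseline is judged after the baseline fallback.* Patients with no derived baseline drop out of the analysis. Everyone left is in the set because Week 24 is missing, so no Week 24 value is observed and the MMRM cannot estimate the Week 24 contrast.
- *Missing at baseline means no Visit 2 value, whatever was measured earlier.* A few members might have a Visit 1 value as baseline and an observed Week 24 result. A contrast might then be estimable, but from a handful of patients.

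The analysis is unusable in both cases.

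**The case against.** The strongest reply is that nobody would program the literal reading. The revision history of the same SAP gives the purpose of the item as exclusion, and it explains the text now in force. Item (e) is a bare noun phrase that does not complete the opening of the list, so it looks like an exclusion label pasted into an inclusion list. A PP set defined by missing outcome data would defeat its own analysis, and a near-empty set would probably be noticed at the first run. The definition also refers to the TIMP. SAP Section 5.2.6 says that plan holds the detailed criteria for important protocol deviations, with programming specifications stored before database lock. Either document may have the rule right.

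All of this stands as a limit on severity. It does not make the sentence correct: the operative definition still contradicts its stated purpose, and the SAP alone does not yield the intended set without a correction by the reader.

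Two stronger readings are tempting, and the documents do not support them.

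- A reader might infer that item (e) conflicts with the baseline rule, so that a patient with a Visit 1 but no Visit 2 HbA1c would be called missing. SAP Section 5.2.1 says: "If baseline data are missing, the last measurement taken prior to this visit will be used for the baseline measurement". Baseline therefore already includes the fallback value, and no text says such a patient counts as missing. A cross-reference would be useful, but there is no contradiction.
- A reader might infer that the Week 24 contrast could not be estimated under any literal reading. That holds only if the fallback value counts as nonmissing, as the working shows.

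**Conclusion.** The drafting error is real and sits in the current SAP text. Followed literally together with (b), the PP set would be about 2 to 45 patients instead of about 405 to 448, and the supportive noninferiority MMRM on it would be unusable. These counts rest on 450 completers as planned and on an assumed 0.5% to 10% with missing HbA1c. They take no account of losses to items (a), (c) and (d).

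The reach is limited. Noninferiority is declared from the MMRM on the FAS, so the primary conclusion, the gated reverse comparison and the sample size do not depend on this item. Only the PP analysis of the primary outcome and the PP baseline summaries do. The documents do not show that the set will be built wrongly: the intent is recoverable from the revision history, and the TIMP and programming specification were not available to check. The sentence should be corrected, but it does not threaten the trial's main result.

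**What to change.** Reword item 4(e) as: *have a nonmissing baseline HbA1c (as derived under the baseline rule in Section 5.2.1) and a nonmissing observed Week 24 (Visit 18) HbA1c*.

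This restores the direction of the rule and makes clear that the fallback baseline counts. The word *observed* keeps a carried-forward 24-week endpoint from satisfying the condition. The present qualifier about subjects due at Visit 18 can go: item (b) already limits the set to patients who have not discontinued before 24 weeks.

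Then check that the TIMP and the analysis-dataset specification for protocol deviations state the rule the same way. The cost is one sentence and that check, best done before database lock. No change to the primary analysis, the sample size or data collection is needed.
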